### **4.2.3 Pharmacokinetic-Evaluable Population (PK Population)**

The PK population includes all patients who have received at least one dose of emicizumab and have at least one post-baseline concentration result.

### **4.2.4 Up-Titrated Population**

This population includes patients who have received at least one dose up-titrated to 3 mg/kg.

### **4.2.5 Surgery Population**

This population includes patients who received at least one dose of emicizumab and have at least one surgical surgery during study conduct (i.e. while receiving emicizumab).

## **4.3 ANALYSIS OF STUDY CONDUCT**

A clear account of all patients who enrolled in the study and who entered, discontinued, and completed the initial and maintenance phases of the study will be displayed.

The reasons for premature discontinuation from study treatment and the reasons for study withdrawal will be described in listings and summary tables.

In addition, the number of patients who received dose up-titration will also be described.

Enrollment, major protocol deviations and reasons for early discontinuation will be listed and evaluated for their potential effects on the interpretation of study results. The type of

major protocol deviations and the number of patients with at least one major protocol deviation will be summarized in terms of both the safety and ITT populations. Major protocol deviations related to COVID-19 will be summarized and listed.

Patient disposition table describes the flow of patients through the study up to the cutoff. Patients will be tabulated with:

- Number of patients enrolled
- Number of patients who discontinued prematurely prior to Study day 1
- Number of patients with duration of efficacy period <2 years
- Number of patients who completed 24 months in the study (efficacy period)
- Number of patients with at least one dose up-titration (up-titrated population)
- Number of patients who started safety follow-up (for interim analyses only)
- Number of patients who completed safety follow-up
- Number of patients who discontinued treatment
- Number of patients who discontinued from the study
- Number of patients who completed the study

Number of patients included and excluded from each analysis population is listed and summarized. All analysis populations defined for the study are included.

Major protocol deviations are listed and summarized by category and type of deviation.

A listing of investigators is produced with a column indicating the number of patients enrolled. Also enrollment will be summarized by country and investigator number. Observation time, duration of efficacy period and duration of follow-up (as defined in section 4.1) are summarized descriptively (unit weeks) and categorically (cumulative): >0 week, ≥4 weeks, ≥12 weeks, ≥24 weeks, ≥36 weeks, ≥48 weeks, ≥72 weeks, ≥96 weeks.

#### **4.4 BASELINE AND DEMOGRAPHIC CHARACTERISTICS**

The following baseline and demographic characteristics will be presented using appropriate descriptive statistics:

For each variable (continuous or categorical), the number of available observations will be reported.

Demographics: demographic information collected at baseline (including age, sex, and self-reported race, ethnicity, height, weight, BSA and BMI). The age will be presented as continuous and categorical (≥12-<18 years, ≥18- <65 and ≥ 65 years) variable. Medical history and Baseline conditions assessment: number and percentage of patients with at least one medical condition and number and percentage of patients by system organ class and preferred term will be presented. Separate summaries will be presented for active and past medical history, where active is defined as ticked on eCRF as ongoing (with or without treatment) and past is defined as ticked as resolved. A listing of all previous and concurrent medical history will also be provided.

Hemophilia history: The following characteristics of the hemophilia history will be presented using appropriate descriptive statistics:

- Hemophilia severity at baseline
- Time from Factor VIII inhibitor diagnosis date (months)  
= (Date of Day 1 - Date of FVIII inhibitor diagnosis)/month  
(continuous and categorical: <24 months, 24-<48 months, 4-<72 months, >=72 months)
- Highest historical inhibitor titer (continuous and categorical: <5 BU, >=5 BU, Unknown)
- Number of patients who already had treatment with ITI
- Time from start of most recent ITI date (years)  
= (Date of Day 1 - Date of Start date of most recent ITI treatment)/year  
(continuous and categorical (< 2 years, 2 – 5 years, >5 years, Unknown))
- Prior episodic treatment in the last 24 weeks
  - Prior prophylactic treatment in the last 24 weeks
  - Reason for not being on prophylactic treatment regimen
- Number of bleeds in last 24 weeks
- Number of target joints prior to study

In addition, the baseline and demographic characteristics will also be summarized on the subset of patients with at least one surgical procedure during study conduct.

Surgery and procedures:

All surgeries and procedures collected on the eCRF page for Surgery and Procedure History Assessment will be listed. In case surgeries are coded, previous surgeries and procedures will in addition be summarized in a frequency table.

#### **4.5 PREVIOUS AND CONCOMITANT MEDICATIONS**

Use of prior and concomitant medication will be presented by medication class and standardized medication name. Number and percentage of patients and number of medications will be presented. Summary tables on concomitant medications will include all dates (before and after up-titration).

A medication is considered concomitant if the start date/time is on or after the date/time of Original Study Day 1. Otherwise, a medication is considered prior if the end date/time is not missing and is before the date/time of Original Study Day 1. Otherwise a medication is considered prior-concomitant.

All hemophilia medication (collected on the electronic handheld device or the site data entry system) will be reported separately. The number of doses and the cumulative doses will be summarized by category of hemophilia medication. Summary tables for hemophilia medications will include data up to the up-titration (if any) only. If at least 10 patients are up-titrated then the frequency table will also be produced on the period after up-titration.

Also all prior episodic and prophylactic hemophilia medication collected on the hemophilia history page will be summarized separately.

## **4.6 EFFICACY ANALYSIS**

This is a single arm study and, consequently, no formal treatment group comparisons will be conducted.

The efficacy analyses will be based on the ITT population. Efficacy analyses will be restricted to the period before up-titration, if any, except if stated otherwise.

### **4.6.1 Efficacy endpoints**

The analysis of efficacy endpoints will be based on the efficacy period defined in Section 4.1.

#### **4.6.1.1 Bleeds**

The primary analysis will be based on treated bleeds (see definition 2.2.2.2). The number of bleeds over time will be estimated using a negative binomial (NB) regression model, which accounts for different follow-up times. The time that each patient stays in the study (efficacy period) will be included as an offset in the model.

An additional model which adjusts for number of bleeds (< 9 or ≥ 9, according to eCRF) in the last 24 weeks prior to study entry will be used to support the primary analysis.

In the rare case that the negative binomial model does not converge or no bleeds were observed for a given endpoint, the primary analysis will be based on “calculated” annualized bleed rate (ABR).

The ABR is calculated using the following formula (called Calculated ABR on all outputs):

$$\frac{\text{Number of bleeds during the efficacy period}}{\text{Number of days during efficacy period}} \times 365.25$$

The efficacy analyses will include the following endpoints defined in section 2.2.2: treated bleeds, all bleeds, treated joint bleeds, treated target joint bleeds and treated spontaneous bleeds. For each endpoint, the model based ABR will be estimated along with its corresponding 95% CI. In addition, the mean, 95% CI based on Exact Poisson, median, IQR, min and max will be provided for the calculated ABR.

A corresponding listing will be provided which will include for each patient the duration of efficacy period, number of bleeds together with calculated ABR for treated bleeds, all bleeds, treated spontaneous bleeds, treated joint bleeds and treated target joint bleeds (based on data before up-titration only). A separate listing will also be provided for the up-titrated population, based on data on or after the up-titration.

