## **4. STATISTICAL METHODS**

No formal statistical hypothesis tests will be performed and all analyses are considered descriptive.

Categorical data will be summarized using frequencies and percentages (including a category for missing, if appropriate). Continuous data will be summarized using descriptive statistics (N, mean, standard deviation, median, lower quartile, upper quartile, minimum and maximum). Other analysis methods will be specified (below) where applicable.

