
Efficacy periods:

The start of the efficacy period for each individual starts on the date of first emicizumab treatment. The end of the efficacy period is defined as the date of the clinical cutoff or the date of withdrawal from/completion of the treatment whichever is earlier.

For patients who withdraw from the study before reaching the Week 1 visit, the duration of efficacy period is set to 1 day, and it starts and ends on the day of enrollment.

For patients whose dose is up-titrated, the efficacy period ends one day prior to the first day on the up-titrated dose (Efficacy period 1).

For patients whose dose is up-titrated, the bleeds occurring during the administration of the up-titrated dose are analyzed separately. The efficacy period on the up-titrated dose starts with the first day on this dose and ends on the day of the clinical cutoff or the date of withdrawal from/completion of treatment (Efficacy period 2).

For statistical evaluations (e.g. descriptive summaries) of post-baseline data summarized by visit, only measurements at scheduled visits are considered. If a measurement is repeated at a scheduled visit (or time point), then only the latest retest result will be used in calculation of the statistical summary. All data – including unscheduled measurements – will be included in the listings.

If a time interval was calculated in minutes, hours or days and needs to be converted into months or years the following conversion factors will be used:

1 year = 365.25 days

1 month = 30.4375 days

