#### **4.6.5 Exploratory Efficacy Endpoints**

Analysis on 12- and 24-week interval:

Additional analysis of the calculated ABR and the number of patients with zero bleeds will be performed for 12- and 24-week intervals on treated bleeds, all bleeds, treated spontaneous bleed, treated joint bleeds and treated target joint bleeds. The 12/24-week intervals are based on the start and end of the Efficacy Period. A patient has only as many 12/24-week intervals as fully fit into this period. E.g. if the duration of Efficacy Period is 98 days (=14 weeks) he has one full 12-week interval and no full 24-week interval. A bleed is assigned to a certain 12/24-week interval based on the distance between bleed date and start of efficacy period. If a bleed is after the end of the last full interval it is not taken into account.

The calculated ABR for a 12/24-week interval will be derived using the following formula which is based on the general formula:

$$\frac{\text{Number of bleeds during the 12 or 24 – week interval}}{84 \text{ or } 168 \text{ days}} \times 365.25$$

The calculated ABRs will be summarized and a graph for the 12- and 24-week intervals for all subjects will be provided. The table will include the mean with the 95% CI based on Exact Poisson, the median with the IQR and the minimum and maximum.

The number of subjects with zero bleeds within a 12- or 24-week interval will be summarized separately and a graph for all subjects will be provided. The table will include the number and percentage of the subjects with zero bleeds and the 95% CI using the Clopper-Pearson method.

The same analysis as described above may also be performed on 36-, 48-, 60- and 72- and 98-week interval if sufficient number of patients available.

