#### **4.6.6 Sensitivity Analyses**

The sensitivity analyses will include different methods to define bleeds or eligible bleed data and different statistical models and will be applied to all efficacy endpoints defined in section 4.6.1.1.

Different ways to define bleeds or eligible bleed data:

- Include all bleeds recorded: without the 72-hour rule and “treated bleeds” but excluding bleed due to surgery and procedure
- Include only patients who received at least 12 weeks of emicizumab treatment, i.e. efficacy period  $\geq 12$  weeks
- Include only the first 24 weeks of efficacy period in the analysis. The calculated ABR is based on Bleeds that occurred before or on day 168 from efficacy period start. Withdrawals are included for the time they were followed for. The 24 weeks Efficacy Period ends 168 days after efficacy period start, the Cut-off date, the date of withdrawal or the end date of efficacy period 1, whichever comes first.

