### Adverse event rate per 100 patient-years

Adverse events per patient years will be calculated for all grade AEs, SAEs, grade  $\geq 3$  AEs, TMA, thromboembolic events (TE) and TMA+TE combined. For each category of events, multiple occurrences of the same event (Preferred term) in the same patient will be counted multiple times.

The adverse event rate per 100 patient-years is computed as follows:

$$\text{AE Rate} = (\text{Number of AEs observed} / \text{Total patient-years at risk}) * 100$$

Total patient years is computed as follows:

Total patient-years at risk is the sum over patients of the time intervals (in years) between start of study therapy (study day 1) and the end of follow up or up to the cutoff whichever is earlier. This approach assumes that during an adverse event, patients remain at risk for additional events.

The 95% confidence interval for the event rate is calculated using the following method. Assume that we observe Y events over a total of T person-years at risk.

Exact confidence interval:

If  $\text{chisq}(p, df)$  is the quantile of the upper tail probability of the  $\chi^2$  distribution on df degrees of freedom, then the lower and upper bounds (LB, UB) of the exact  $(1 - \alpha/2)$  level interval are given by:

$$\text{LB} = \text{chisq}(p = \alpha/2, df = 2Y) / (2T)$$

$$\text{UB} = \text{chisq}[p = 1 - \alpha/2, df = 2(Y + 1)] / (2T)$$

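### The Exact Poisson 95% CI on the mean calculated ABR names no count or exposure, and on the pooled reading it is too narrow for bleed counts that the SAP itself models as negative binomial

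*SAP*

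**What the plan says.** SAP 4.6.1.1 estimates bleed rates with a negative binomial model that has the efficacy period as offset, and reports its 95% CI for each endpoint. Next to it stands a calculated ABR, defined per patient as bleeds divided by days, times 365.25. For this the SAP says: "the mean, 95% CI based on Exact Poisson, median, IQR, min and max will be provided for the calculated ABR". The calculated ABR becomes the primary bleed analysis "In the rare case that the negative binomial model does not converge or no bleeds were observed for a given endpoint".

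SAP 4.6.5 repeats the method by interval: "The table will include the mean with the 95% CI based on Exact Poisson, the median with the IQR". Exposure is equal there, because "A patient has only as many 12/24-week intervals as fully fit into this period". In 4.6.1.1 it is not equal: patients withdraw, and under SAP 4.1 "For patients whose dose is up-titrated, the efficacy period ends one day prior to the first day on the up-titrated dose".

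SAP 4.6.7 asks for a 95% CI on the calculated mean ABR by subgroup and names no method. The only exact Poisson formula written out is in SAP 4.9.2, for adverse event rates: "Assume that we observe Y events over a total of T person-years at risk". Nothing ties it to the ABR.

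**The concern.** An exact Poisson interval needs an integer count and an exposure. A mean of per-patient rates is neither, so two programmers could follow the same sentence and print different intervals.

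The second difficulty is the distribution. Exact Poisson limits on a pooled total assume that all patients share one bleed rate. Choosing a negative binomial model says that they do not. If the pooled interval is used, the 12- and 24-week tables, which are meant to show bleed control over time, would carry intervals that understate the uncertainty, and adding patients does not cure this. In 4.6.1.1 the pooled interval would also be centred on a different quantity from the mean printed beside it.

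**Working it through.** The plan gives no numerical value for this interval, so there is no figure to reproduce.

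**Inputs from the documents.** N about 200; two-year treatment; intervals of 84 and 168 days. From Protocol 1.2.2.3 and 3.3.1 (BH29884, emicizumab arm, N = 35): treated bleeds 2.9 (1.7, 5.0), treated joint bleeds 0.8 (0.3, 2.2), treated target joint bleeds 0.1 (0.03, 0.6), and 22 of 35 (63%) with zero treated bleeds. Minimum follow-up there was 24 weeks.

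**Assumptions.** 52 weeks as the upper follow-up in that study, with equal follow-up per patient; ABR 0.5 and 1.0 as lower rates; k = 2 as the central dispersion.

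**Step 1, dispersion.** With μ = ABR × t, Var(log rate) = (1/μ + k)/N, so k = N × SE² − 1/μ, where SE = ln(upper/lower)/3.92.
- Treated bleeds: SE = ln(5.0/1.7)/3.92 = 0.275. At 24 weeks μ = 2.9 × 168/365.25 = 1.334, so k = 2.65 − 0.75 = 1.90. At 52 weeks k = 2.30.
- Treated joint bleeds: SE = ln(2.2/0.3)/3.92 = 0.508. At 24 weeks μ = 0.368, so k = 9.04 − 2.72 = 6.3 (4.6 to 8.4 allowing for rounding).
- Treated target joint bleeds: k is negative at 24 weeks, so these rounded figures cannot show overdispersion.
- Cross-check: one common Poisson rate predicts exp(−1.334) = 26% with zero treated bleeds at 24 weeks. The negative binomial with k = 1.9 predicts 51%. The study reported 63%.

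**Step 2, pooled reading.** Limits are χ²(0.025; 2Y)/(2T) and χ²(0.975; 2Y + 2)/(2T), with Y total bleeds and T total patient-years. The interval is too short by about √(1 + k × ABR × t), whatever N is. For ABR 2.9 and k = 2 this is 1.53 at 12 weeks and 1.92 at 24 weeks. At the expected counts for N = 200, Poisson against dispersion-adjusted limits are 2.43–3.44 against 2.24–3.76 (12 weeks) and 2.56–3.27 against 2.30–3.65 (24 weeks).

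Simulated coverage of the nominal 95% interval (gamma-Poisson counts, N = 200):

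| ABR, k | 12 weeks | 24 weeks | Two years |
|---|---|---|---|
| 2.9, k = 2 | about 80% | about 71% | 41–43% |
| 1.0, k = 2 | about 91% | about 85% | about 63% |
| 0.5, k = 2 | 94% | 91% | – |
| 0.8, k = 6.3 (joint) | – | about 73% | – |

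For k from 1 to 3 at ABR 2.9 the range is 88–75% at 12 weeks and 80–63% at 24 weeks. A log-link Poisson model with robust variance covers 94–95% at N = 200 for ABR 0.5 to 2.9 and k up to 3.

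**Step 3, centring in 4.6.1.1.** Constructed example: 190 patients have 2 bleeds in 2 years and 10 have 5 bleeds in 0.25 year. The mean of per-patient ABRs is (190 × 1 + 10 × 20)/200 = 1.95. The pooled rate is 430/382.5 = 1.12, with exact limits 1.02–1.24, which exclude the reported mean. With 10% or 20% of patients leaving at random (ABR 2.9, k = 2), this happens in 3% and 7% of simulated trials.

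**Step 4, single-count reading.** With the mean as the count and exposure 1, the limits are 0.58–8.62 at 2.9 and 0.03–5.57 at 1.0 for any N. Coverage at N = 200 is about 100%.

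**Step 5, no bleeds.** With 200 × 2 = 400 patient-years the upper limit is 0.009 per year on the pooled reading and 3.69 per year on the single-count reading.

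**The case against.** The strongest reply is about weight. The SAP says: "No formal statistical hypothesis tests will be performed and all analyses are considered descriptive". Bleeds are a secondary objective, the interval tables are exploratory, the negative binomial CI stands beside the calculated ABR in both 4.6.1.1 and 4.6.7, and the SAP itself calls its fallback rare. For one window, 4.6.6 ("Include only the first 24 weeks of efficacy period in the analysis") may supply a model-based interval. All of this stands and limits the consequence. It does not reach the later 12- and 24-week intervals, for which no model-based CI is planned.

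A reader might infer that nobody could tell which interval was printed. That is not supported. The two readings differ about tenfold in width, and the per-patient listing in 4.6.1.1 allows that summary to be recomputed. Recognising the interval afterwards does not make it calibrated, though.

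A reader might also infer that every reading understates the uncertainty. At N = 200 the single-count interval over-covers; its fault is that it ignores N. A third conceivable reading, the sum of per-patient ABRs over N, does under-cover: 58% at two years for ABR 2.9 and k = 1.9.

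It can be argued that low-rate endpoints are safe. This holds only with modest dispersion. Treated joint bleeds have a low rate and still reach only about 73% at 24 weeks.

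Finally, 4.6.7 names no method, so extending the defect to the subgroups is conjecture. There the point is only that the method should be named.

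**Conclusion.** The point holds as a minor-to-moderate correction. The interval is undefined as written, and the pooled reading, the only one with a formula elsewhere in the SAP, gives intervals too short by a factor of about 1.5 at 12 weeks and 1.9 at 24 weeks for treated bleeds at the earlier study's rate. These sizes rest on that rate and dispersion carrying over to this trial. At an assumed ABR of 0.5 with k = 2 the shortfall nearly disappears at 12 and 24 weeks, and nothing can be shown for treated target joint bleeds at 24 weeks.

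Affected are the supportive calculated-ABR summary, the 12- and 24-week tables, and the fallback when the negative binomial model does not converge although bleeds occurred. A reader might conclude that the trial's main bleed-rate estimate or its safety conclusions are unreliable. The documents do not support that: the negative binomial interval is unaffected, and no decision rule uses the Poisson one.

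**What to change.** 1. In 4.6.5, replace Exact Poisson with a log-link Poisson model with robust (sandwich) variance, fitted per interval.
2. In 4.6.1.1, state whether the pooled rate or the mean of per-patient ABRs is reported. For the pooled rate use the same robust model with a log(time) offset, also in the non-convergence fallback when bleeds were observed. For the mean of per-patient ABRs use a patient-level bootstrap.
3. Name the same method in 4.6.7.
4. Keep the exact Poisson upper limit, on total person-time, only where no bleeds are observed.

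The cost is SAP wording in two sections, one phrase in 4.6.7, and a standard procedure; no new data are needed. Some intervals become wider. In small subgroups the robust interval is still short (k = 2: about 92–93% at an assumed N = 30, and 88–89% at N = 10 over two years), but much closer to 95% than the pooled Poisson interval (42% at N = 30 over two years for ABR 2.9; 64% at N = 10 for ABR 1.0). The bootstrap may also fall slightly short if many patients are truncated at up-titration because of bleeds: it covered 91% in one run that assumed 10% leaving and truncation at the second bleed for 20% of patients with two or more.

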#### **4.6.1.2 Number of Bleeds/ABR categories**

Number of patients with 0, 1-3, 4-10, >10 bleeds as well as number of patients with calculated ABR <1, 1-3.4, 3.5-10, >10 will be summarized. Figures including 95% CI will also be provided. All summaries and figures will be produced for treated bleeds, all bleeds and treated spontaneous bleeds.

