### **2.3 DETERMINATION OF SAMPLE SIZE**

A sample size of approximately 200 patients is planned for this study.

For the purpose of the sample size calculation, the incidence of adverse events was chosen as the safety endpoint of primary interest.

If the observed incidence of adverse events is between 2.5% and 15%, the precision for the estimated incidence rate is presented below according to the 95% Clopper-Pearson confidence intervals (CIs) (Table 1).

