### **2.4 ANALYSIS TIMING**

The first interim analysis will be performed once approximately 100 patients have received treatment with emicizumab for at least 24 weeks.

A second interim analysis will be performed when approximately 100 patients have received treatment with emicizumab for at least 52 weeks.

The data from these analyses will subsequently be presented to the independent Data Monitoring Committee (iDMC) in order to enable them to effectively monitor the study (see Section 3.3).

Given the hypothesis-generating nature of this study, the Sponsor may choose to conduct up to two additional interim efficacy analyses (i.e., beyond what is specified in Section 6.9.1 of the clinical study protocol [CSP]).

The final analysis will be conducted when all patients have completed 2 years of treatment or have withdrawn, whichever occurs sooner.

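### The zero-bleed share in SAP 4.6.1.2 pools efficacy periods of unequal length in a consent-based ITT set, so early withdrawals, undosed patients and (in interim tables only) data cutoffs push it upward

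*SAP*

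**What the plan says.** - **The table.** SAP 4.6.1.2: "Number of patients with 0, 1-3, 4-10, >10 bleeds as well as number of patients with calculated ABR <1, 1-3.4, 3.5-10, >10 will be summarized". It is produced for treated, all, and treated spontaneous bleeds, with figures showing 95% CIs. No minimum or common window is set.
- **The window.** SAP 4.6.1 uses the efficacy period of SAP 4.1, which starts at first dose. "The end of the efficacy period is defined as the date of the clinical cutoff or the date of withdrawal from/completion of the treatment", taking the earlier date. For an up-titrated patient it stops the day before the higher dose. For a patient who withdraws before the Week 1 visit, "the duration of efficacy period is set to 1 day, and it starts and ends on the day of enrollment".
- **The denominator.** SAP 4.6 uses the ITT population, which SAP 4.2.2 defines by signed consent, dosed or not.
- **The cutoffs.** SAP 2.4: "The first interim analysis will be performed once approximately 100 patients have received treatment with emicizumab for at least 24 weeks". Nothing limits the interim table to those 100 patients. The final analysis waits until every patient has finished two years or withdrawn.
- **Related analyses.** The main bleed model (4.6.1.1) has the efficacy period as an offset. Section 4.6.5 gives zero-bleed percentages in complete 12- and 24-week intervals, with longer intervals optional. Section 4.6.6 adds a set with at least 12 weeks and a first-24-weeks analysis, both tied to the 4.6.1.1 endpoints. Section 4.3 summarizes efficacy-period duration.

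**The concern.** A raw count depends on how long the patient was watched. The SAP allows for this in the main bleed model but not in the count table. Someone who leaves at week 4 without a bleed, and someone who consented but never received emicizumab, sit in the same cell as a bleed-free two-year completer. The calculated-ABR classes in the same sentence do not help: zero bleeds over any period gives an ABR of 0, which falls in the lowest class.

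The share with zero bleeds is easily quoted. The protocol reports it for both earlier studies (Section 1.2.2.3). Here the figure, with its CI, would partly reflect the follow-up mix and the number of undosed patients rather than the effect of treatment.

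**Working it through.** **Plan's own figures.** The SAP gives no expected zero-bleed share. Its only precision figures are the Clopper-Pearson intervals at N=200 in Section 2.3, and all four rows reproduce. The anchor share also reproduces: 22/35 = 62.9% (44.9, 78.5).

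**Inputs.** From the protocol's table for the earlier randomized trial, emicizumab arm, N=35: treated-bleed ABR 2.9 and 62.9% with zero treated bleeds. Follow-up there was at least 24 weeks with no mean stated, so 24 and 30 weeks are both tried.

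**Model.** Each patient has a constant rate, gamma-distributed across patients (negative binomial). With μ = 2.9 per year and t in years:

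P0(t) = (1 + kμt)^(-1/k)

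Setting P0 = 0.629 gives k = 3.97 (24-week anchor) or 4.70 (30-week anchor). Check at 104 weeks, 24-week anchor: μt = 2.9 × 728/365.25 = 5.78, and (1 + 3.97 × 5.78)^(-1/3.97) = 0.449.

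| Window | Zero-bleed, 24-wk anchor | Zero-bleed, 30-wk anchor |
|---|---|---|
| 4 wk | 85% | 86% |
| 12 wk | 72% | 74% |
| 24 wk | 63% | 66% |
| 52 wk | 53% | 57% |
| 104 wk | 45% | 49% |

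Only the window changes between rows. The share with more than 10 bleeds moves the other way, from 2% (3%) at 24 weeks to 17% (16%) at 104 weeks. Below, 30-week-anchor results are in brackets.

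**Final analysis, withdrawals (assumed 5, 10, 20%, evenly spread over two years).** The average of P0 over 0-104 weeks is 56.8% (60.1%). At 20%: 0.8 × 44.9 + 0.2 × 56.8 = 47.3%. The three cases give 45.5, 46.1 and 47.3%, against 44.9% at a common 104 weeks (49.7, 50.2 and 51.3% against 49.1%). That is +0.6 to +2.4 points. If every leaver went at week 12, it would be +1.3 to +5.5 points.

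**Final analysis, undosed patients (assumed 2 to 20 of 200).** Each counts as zero-bleed. For 2: (198 × 0.449 + 2)/200 = 45.5%. For 20: (180 × 0.449 + 20)/200 = 50.4%. That is about +0.5 to +5.5 points.

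**First interim (accrual assumed: 50-100 further patients spread over 0-24 weeks).** If the first 100 have exactly 24 weeks, the table shows 67-69% (69-71%) against 62.9% (65.6%) at a common 24 weeks: +3.5 to +6 points. If the first 100 have 24-52 weeks, it shows 63-66% (66-68%): about 0 to +3 points.

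**Second interim (100 patients at 52-78 weeks and 100 at 24-52, assumed).** 53.8% (57.3%) against 52.9% (56.5%) at a common 52 weeks: under 1 point.

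**The case against.** The strongest reply is that the plan already covers most of this. The main estimate uses an exposure offset and is untouched. Section 4.6.5 pre-specifies equal-window zero-bleed percentages with exact CIs, and its exploratory label means little when every analysis is descriptive. Zero-bleed share is not a named endpoint, and efficacy is secondary in a safety study. At the final analysis, 10-20% evenly spread withdrawal adds 1.1-2.4 points, against a standard error of √(0.45 × 0.55/200) = 3.5 points.

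Most of that stands and limits the point. But Section 4.6.5 neither replaces nor corrects the 4.6.1.2 table, and it commits only to 12- and 24-week windows. Section 4.6.6 does not explicitly reach that table. Neither deals with the undosed patients.

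A reader might also infer more than the documents support:

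- **That interim cutoffs inflate the final table.** They cannot. By then each patient has two years or has withdrawn (SAP 2.4).
- **That up-titrated patients become zero-bleed.** Up-titration follows poor bleed control (protocol 4.3.2.1), so these patients have normally already bled. Ending their period early mainly holds them in a lower non-zero class.
- **That 63-66% at the first interim against 45% at two years measures the bias.** Those are different horizons. The fair comparison is a common 24-week window.
- **That the table is uniquely unfit for comparison with the earlier trials.** Their shares also pool unequal follow-up: a 24-week minimum or discontinuation in one, and 12.7-41.6 weeks in the other.

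**Conclusion.** The point holds for the raw count classes, above all the zero class. Ending observation early can only lower a count, so against a common two-year window the zero-bleed share can only be too high. That direction needs no model. Against a shorter common window the net shift depends on the follow-up mix, which is why the first-interim range starts near zero.

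The size is modest: about 0.6-2.4 points from withdrawal at the final analysis, a further 0.5-5.5 points from undosed patients, and 0-6 points at the first interim. These figures rest on an outside arm of 35 patients, a constant rate per patient, withdrawal unrelated to bleeding, and assumed withdrawal, undosed and accrual patterns. The undosed share is the least certain: SAP 4.2.2 equates enrolment with consent, whereas protocol 4.5.1 places it after eligibility is confirmed. The model-based ABR is not affected.

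**What to change.** In SAP 4.6.1.2:

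1. Add the zero-bleed share at 24, 52 and 104 weeks by Kaplan-Meier time to first bleed, with 95% CI, in all dosed patients, counted from first dose and censored at the end of the efficacy period. Use this, with the 4.6.5 interval results, for any zero-bleed statement.
2. Keep the raw count table for dosed patients only. Label it as unequal exposure and show efficacy-period duration by class.
3. Do not restrict the count table to patients observed for a full window. An up-titrated patient's efficacy period ends at up-titration, so that would remove patients who have bled and raise the zero share again. If 5% were up-titrated (assumed), 45% would become 45/95 = 47.4%.

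The cost is SAP wording and one extra derivation from data already collected. Kaplan-Meier assumes that withdrawal is non-informative, and the SAP should say so.
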